### 6.3 Outcome variables and study follow-up:

### 6.3.1 Outcome variables

Primary Effectiveness outcomes of interest: (definitions provided in **Appendix A**):

### • Primary Outcome: VTE

Safety outcomes of interest:

1. Major bleeding

#### 6.3.2 Study follow-up

Both as-treated (AT) and intention-to-treat (ITT) analyses will be conducted with treatment defined as the index drug on the day of cohort entry. Because adherence in the real-world databases is expected to be much worse than in the trial, the AT analysis is the primary analysis, as it targets the relative hazard of outcomes on treatment.

For the AT analyses, the follow-up will start the day after initiation of rivaroxaban and comparator and will continue until the earliest date of the following events:

- The first occurrence of the outcome of interest, unless otherwise specified for selected outcomes,
- The date of end of continuous registration in the database,
- End of the study period,
- Measured death event occurs,
- Nursing home admission
  - Nursing home admissions are considered a censoring event because the data sources utilized typically provide little to no data on a patient, particularly on drug utilization, after admission. We will utilize this as an exclusion reason for cohorts for the same reason.
- The date of drug discontinuation, defined as the date of the last continuous treatment episode of the index drug (rivaroxaban and comparator) plus a defined grace period (i.e., 10 days after the end of the last prescription's days' supply in main analyses).
- The date of augmentation or switching from exposure to comparator or vice versa or augmentation/switching to any other NOAC (e.g. switching from rivaroxaban to apixaban would be a censoring event);
  - $\circ~$  A dosage change on the index treatment does not fulfill this criterion
  - o An added treatment that is not part of the exposure or comparator group does not fulfill this criterion

For the intention-to-treat (ITT) analyses, the censoring based on the augmentation/switching and treatment discontinuation will be replaced with a maximum allowed follow-up time of 365 days.

#### 7. Initial Feasibility Analysis

Aetion report name:

Optum- https://bwh-dope.aetion.com/projects/details/1482/results/64422/result/0 MarketScan- https://bwh-dope.aetion.com/projects/details/1480/results/64423/result/0 Medicare- https://bwh-dope.aetion.com/projects/details/1479/results/64424/result/0

### Date conducted: 1/15/2021

Complete Aetion feasibility analysis using age, sex, and CCI as the only covariates and the primary endpoint (Section 6.3.1) as the outcome. No measures of association will be computed nor will incidence rates stratified by treatment group.

- Report patient characteristics by treatment group
- Report summary parameters of study population
- Report median follow-up time by treatment group
- Report reasons for censoring in the overall study population

### 8. Initial Power Assessment

#### Aetion report name:

For rivaroxaban vs. warfarin Optum- https://bwh-dope.aetion.com/projects/details/1482/results/63169/result/0 MarketScan- https://bwh-dope.aetion.com/projects/details/1480/results/63168/result/0 Mediare- https://bwh-dope.aetion.com/projects/details/1479/results/63200/result/0

### Date conducted: 12/22/2020 (Medicare 12/23/20)

In order to complete the initial power analysis, the dummy outcome of a 90-day gap in database enrollment will be used. This outcome is used to ensure that no information on the comparative risks of the outcomes of interest are available at this stage. Complete a 1:1 PS-matched comparative analysis using this outcome. PS should include only 2 covariates: age and combined comorbidity index. Power calculations are based on the formulas from Chow et al. (2008).

- Stop analyses until feasibility and power are reviewed by primary investigators and FDA. Reviewers evaluate the results of the analyses described above in Sections 7 and 8, including numbers of patients, patient characteristics, follow-up time, and reasons for censoring by treatment group, as well as overall rates of outcomes and study power. These parameters are re-evaluated and reported in the subsequent sections, after incorporating feedback and refining the protocol.
- Stop analyses until balance and final power assessment are reviewed by primary investigators, FDA, and assigned members of advisory board.

Reviewed by PI:	[name]	Date reviewed:	11/18/2020
Reviewed by FDA:	[name]	Date reviewed:	11/29/2020
Reasons for stopping			
analysis (if required):			

#### 9. Balance Assessment

#### Action report links:

Optum: https://bwh-dope.aetion.com/projects/details/1482/results/63187/result/0 Marketscan: https://bwh-dope.aetion.com/projects/details/1480/results/63178/result/0 Medicare: https://bwh-dope.aetion.com/projects/details/1479/results/63202/result/0

### Date conducted: 12/23/20

After review of initial feasibility and power analyses, complete creation of the remaining covariates from Section 6.2. Again, using the dummy outcome of a 90-day gap in database enrollment, complete a 1:1 PS-matched analysis. The PS should include the complete list of covariates.

• Provide plot of PS distributions stratified by treatment group.

Note- Please refer to **Appendix B**.

• Report covariate balance after matching.

Note- For Table 1, please refer to **Appendix B**.

	Overall	Referent	Exposure
Dummy outcome	326 (1.04%)	175 (1.11%)	151 (0.96%)
Death	698 (2.22%)	345 (2.20%)	353 (2.25%)
Start of an additional exposure	1,548 (4.93%)	983 (6.26 %)	565 (3.60%)
End of index exposure	23,549 (74.98%)	11,297 (71.94%)	12,252 (78.02%)
Specified date reached	1,374 (4.37%)	711 (4.53%)	663 (4.22%)
End of patient enrollment	925 (2.95%)	503 (3.20%)	422 (2.69%)
Switch to other NOACs (for censoring) + nursing home admission	2,988 (9.51%)	1,690 (10.76%)	1,298 (8.27%)

#### • Report reasons for censoring by treatment group.

#### • Report follow-up time by treatment group.

Median Follow-Up Time (Days) [IQR]						
Patient Group Optum Marketscan Medicare						
Overall Patient Population	59 [29-131]	73 [38-146]	73 [38-154]			
Referent	64 [28-138]	78 [38-150]	82 [38-165]			
Exposure	54 [29-126]	67 [38-141]	65 [38-139]			

### • Report overall risk of the primary outcome.

	Optum	Marketscan	Medicare	Pooled
Risk per 1,000 patients	17.57	18.15	18.96	18.54

### **10. Final Power Assessment**

### Date conducted: 12/23/20

• Re-calculate power in the appropriate excel table, using the revised number of matched patients from the PS-match in Section 9. All other parameters in the table should be the same as in Section 8.

• Pooled

Superiority Analysis		Non-inferiority Analysis	
Number of patients matched	25,970	Number of patients matched	25,970
Reference	12,985	Reference	12,985
Exposed	12,985	Exposed	12,985
Risk per 1,000 patients	18.54	Risk per 1,000 patients	18.54
Desired HR from RCT	0.68	Assumed HR from RCT	1
Alpha (2-sided)	0.05	Alpha (2-sided)	0.05
		Non-inferiority margin	2
Number of events expected	481.4838	Number of events expected	481.4838
Power	0.988435033	Power	0.999999992

o Optum

Effectiveness research with Real World Data to support FDA's regulatory decision making

Superiority Analysis		Non-inferiority Analysis	
Number of patients matched	3,150	Number of patients matched	3,150
Reference	1,575	Reference	1,575
Exposed	1,575	Exposed	1,575
Risk per 1,000 patients	17.57	Risk per 1,000 patients	17.57
Desired HR from RCT	0.68	Assumed HR from RCT	1
Alpha (2-sided)	0.05	Alpha (2-sided)	0.05
		Non-inferiority margin	2
Number of events expected	55.3455	Number of events expected	55.3455
Power	0.299994744	Power	0.731829277

#### • Marketscan

[		[	
Superiority Analysis		Non-inferiority Analysis	
Number of patients matched	5,798	Number of patients matched	5,798
Reference	2,899	Reference	2,899
Exposed	2,899	Exposed	2,899
Risk per 1,000 patients	18.15	Risk per 1,000 patients	18.15
Desired HR from RCT	0.68	Assumed HR from RCT	1
Alpha (2-sided)	0.05	Alpha (2-sided)	0.05
		Non-inferiority margin	2
Number of events expected	105.2337	Number of events expected	105.2337
Power	0.507287833	Power	0.944678362

• Medicare

Superiority Analysis		Non-inferiority Analysis	
Number of patients matched	17,022	Number of patients matched	17,022
Reference	8,511	Reference	8,511
Exposed	8,511	Exposed	8,511
Risk per 1,000 patients	18.96	Risk per 1,000 patients	18.96
Desired HR from RCT	0.68	Assumed HR from RCT	1
Alpha (2-sided)	0.05	Alpha (2-sided)	0.05
		Non-inferiority margin	2
Number of events expected	322.73712	Number of events expected	322.73712
Power	0.933738593	Power	0.999990058

• Stop analyses until balance and final power assessment are reviewed by primary investigators, FDA, and assigned members of advisory board.

Reviewed by PI:	[name]	Date reviewed:	12/24/2020
Reviewed by FDA:	[name]	Date reviewed:	01/18/2020
Reasons for stopping			
analysis (if required):			

### **11. Study Confidence and Concerns**

Deadline for voting on study confidence and listing concerns: Date votes and concerns are summarized:

- If final feasibility and power analyses are reviewed and approved, proceed to the remaining protocol steps.
- All study team and advisory board members that review this protocol should at this stage provide their level of confidence for the

success of the RWD study in the Google Form. This form also provides space for reviewers to list any concerns that they feel may contribute to a failure to replicate the findings of the RCT, including differences in study populations, poor measurement of study variables, or residual confounding. All responses will be kept confidential and individual-level results will only be shared with the individual respondent.

• After the deadline for voting has passed, provide the distribution of responses and summarize all concerns here.

### 12. Register study protocol on clinicalTrials.gov

#### Date conducted:

• Register the study on clinicalTrials.gov and upload this document.

#### **13.** Comparative Analyses

#### Aetion report name: Date conducted:

- 13.1 For primary analysis:
- 13.2 For sensitivity analyses:

#### 14. Requested Results

#### 14.1 Table 1: Baseline characteristics before and after adjustment

Variable	Before adjustment			After adjustment		
	Referent	Exposure	Std. diff.	Referent	Exposure	Std. diff.
Number of patients			-			-
Age categories						

### 14.2 Table 2: Follow-up time

Patient Group	Median Follow-Up Time (Days) [IQR]
Overall Patient Population	
Referent	
Exposure	

### 14.3 Table 3: Censoring events

	Overall	Referent	Exposure
Outcome			
Death			
Start of an additional exposure			
End of index exposure			
Specified date reached			
End of patient data			
End of patient enrollment			

### 14.4 Table 4: Results from primary analyses;

Analysis	No. exposed events	No. referent events	Exposed rate	Referent rate	HR (95% CI)
Crude					
Analysis 1					
Analysis 2					

HR, Hazard Ratio; CI, Confidence Interval.

### 14.5 Table 5: Results from secondary analyses;

### 15. References

#	EINSTEIN DVT trial definitions	Implementation in routine care	Please see the following Google Drive for further details or any missing infor https://drive.google.com/drive/folders/1WD618wrywYIEaXrlLTcuK-VCcnb6b-gV7	mation: usp=sharing
	Trial details- Primary approval; Unintended S with label change		Some codes are not listed in this document because of excel cell size limitations and excessive number of ICD-10 codes. Full ICD-10 code lists will be available in the above Google Drive Folder (link above). ICD-9 to ICD-10 code conversions were completed using a SAS macro that implements. forward/backward mapping based on the CMS ICD-9 to ICD-10 mapping: https://www.nber.ore/data/cd9-icd-10-cm-and-pcs-crosswalk-general-gouvalence-mapping.html	
	EXPOSURE vs. COMPARISON		References/Rationale	Color coding
		Rivaroxaban vs. Warfarin		Criteria
	PRIM	ARY OUTCOME		Adequate mapping in claims
	Recurrent thromboembolism defined as the composite of (Deep vein thrombosis) DVT or nonfatal or fatal pulmonary embolism (PE)	Measured 1 day after drug initiation in any diagnosis position and in an inpatient care setting Recurrent VTE (composite of DVT or PE); See 'VTE' sheet for codes	Fang MC, Fan D, Sung SH, et al. Validity of Using Inpatient and Outpatient Administrative Codes to Identify Acute Venous Thromboembolism: The CVRN VTE Study. Med Care. 2017;55(12):e137-e143.	Intermediate mapping in claims
				Poor mapping or cannot be measured

13 Any other contraindication listed in the local labeling of enoxaparin, warfarin, or acenocoumarol	N/A
14 Concomitant use of strong CYP3A4 inhibitors (e.g. HIV protease inhibitors, systemic ketoconazole) or strong CYP3A4 inducers rifampin	Prescription claim for following CYP3A inhibitors or strong CYP3A inducers Measured 14 days prior to and also on the drug initiation date Inhibitors: Ketoconazole, itraconazole, voriconazole, telithromycin, clarithromycin, nefazodone, ritonavir, saquinavir, neffinavir, indinavir, atazanavir Inducers: Rifampin, rifampicin/rifampin, phenytoin, carbamazepine
15 Symptomatic pulmonary embolism	Measured 14 days prior to and including the day of drug initiation in any diagnosis position and in an inpatient care setting as defined below: Pulmonary embolism: ICD-9 Dx: 415.1x ICD-10 Dx: I26.* EXCEPT I26.90

Trial Catergory	Secondary initiation
RCT Category	5a- Successful NI with label change
Trial Name (with web links)	EINSTEIN DVT
Study Batch	NOACs
NCT	NCT00440193
Therapeutic Area	Cardiology/Vascular Diseases
Brand Name	Xarelto
Generic Name	Rivaroxaban
Sponsor	Bayer
Year	2010
Measurable endpoint	Percentage of Participants With Symptomatic Recurrent Venous Thromboembolism [VTE] (i.e. the Composite of
	Recurrent Deep Vein Thrombosis [DVT] or Fatal or Non-fatal Pulmonary Embolism [PE]) Until the Intended End of Study Treatment
Exposure	Rivaroxaban
Comparator	Enoxaparin/VKA
Trial finding	HR = 0.68 (95% CI 0.44–1.04)
No. of Patients	3,449
Non-inferiority margin	HR = 2.0
Finding for potential Assay Sens. Outcome from trial-	HR 0.72, 95% CI 0.53-0.99
Assay Sens. Finding	Percentage of Participants With the Composite Variable Comprising Recurrent DVT, Non-fatal PE and All Cause Mortality Until the Intended End of Study Treatment
Power	0.90. Assuming equal efficacy, a total of 88 events was calculated to give a power of 90% to prove that rivaroxaban is at least as effective as the comparator, considering a non-inferiority upper CI margin for the hazard ratio of 2.0 (two-sided $\alpha$ =0.05). A mean incidence for the primary efficacy outcome of 3% was expected and at least 1465 participants per group were determined to be necessary. This number was to be adjusted based on the observed overall incidence of symptomatic recurrent VTE.

Title	
Venous Thromboembolism (VTE)	
ICD-9 Dx inpatient primary position	
PE	
415.1	PULMONARY EMBOLISM AND INFARCTION
415.11	IATROGENIC PULMONARY EMBOLISM AND INFARCTION
415.19	OTHER PULMONARY EMBOLISM AND INFARCTION
DVT	
451.1	PHLEBITIS AND THROMBOPHLEBITIS OF DEEP VEINS OF LOWER EXTREMITIES
451.11	PHLEBITIS AND THROMBOPHLEBITIS OF FEMORAL VEIN (DEEP) (SUPERFICIAL)
451.19	PHLEBITIS AND THROMBOPHLEBITIS OF OTHER
451.2	PHLEBITIS AND THROMBOPHLEBITIS OF LOWER EXTREMITIES UNSPECIFIED
451.81	PHLEBITIS AND THROMBOPHLEBITIS OF ILIAC VEIN
451.9	PHLEBITIS AND THROMBOPHLEBITIS OF UNSPECIFIED SITE
453	BUDD-CHIARI SYNDROME
453.1	THROMBOPHLEBITIS MIGRANS
453.2	EMBOLISM AND THROMBOSIS OF INFERIOR VENA CAVA
453.4	ACUTE VENOUS EMBOLISM AND THROMBOSIS OF DEEP VESSELS OF LOWER EXTREMITY
453.4	ACUTE VENOUS EMBOLISM AND THROMBOSIS OF UNSPECIFIED DEEP VESSELS OF LOWER EXTREMITY
453.41	ACUTE VENOUS EMBOLISM AND THROMBOSIS OF DEEP VESSELS OF PROXIMAL LOWER EXTREMITY
453.42	ACUTE VENOUS EMBOLISM AND THROMBOSIS OF DEEP VESSELS OF DISTAL LOWER EXTREMITY
453.5	CHRONIC VENOUS EMBOLISM AND THROMBOSIS OF DEEP VESSELS OF LOWER EXTREMITY
453.5	CHRONIC VENOUS EMBOLISM AND THROMBOSIS OF UNSPECIFIED DEEP VESSELS OF LOWER EXTREMITY
453.51	CHRONIC VENOUS EMBOLISM AND THROMBOSIS OF DEEP VESSELS OF PROXIMAL LOWER EXTREMITY
453.52	CHRONIC VENOUS EMBOLISM AND THROMBOSIS OF DEEP VESSELS OF DISTAL LOWER EXTREMITY
453.8	ACUTE VENOUS EMBOLISM AND THROMBOSIS OF OTHER SPECIFIED VEINS
453.82	ACUTE VENOUS EMBOLISM AND THROMBOSIS OF DEEP VEINS OF UPPER EXTREMITY
453.83	ACUTE VENOUS EMBOLISM AND THROMBOSIS OF UPPER EXTREMITY UNSPECIFIED
453.84	ACUTE VENOUS EMBOLISM AND THROMBOSIS OF AXILLARY VEINS
453.85	ACUTE VENOUS EMBOLISM AND THROMBOSIS OF SUBCLAVIAN VEINS
453.86	ACUTE VENOUS EMBOLISM AND THROMBOSIS OF INTERNAL JUGULAR VEINS
453.87	ACUTE VENOUS EMBOLISM AND THROMBOSIS OF OTHER THORACIC VEINS
453.89	ACUTE VENOUS EMBOLISM AND THROMBOSIS OF OTHER SPECIFIED VEINS

453.9	EMBOLISM AND THROMBOSIS OF UNSPECIFIED SITE
ICD-10 Dx inpatient p	rimary position
PE	
126.0	Pulmonary embolism with acute cor pulmonale
126.01	Septic pulmonary embolism with acute cor pulmonale
126.02	Saddle embolus of pulmonary artery with acute cor pulmonale
126.09	Other pulmonary embolism with acute cor pulmonale
126.9	Pulmonary embolism without acute cor pulmonale
126.99	Other pulmonary embolism without acute cor pulmonale
DVT	
180.1	Phlebitis and thrombophlebitis of femoral vein
180.10	Phlebitis and thrombophlebitis of unspecified femoral vein
180.11	Phlebitis and thrombophlebitis of right femoral vein
180.12	Phlebitis and thrombophlebitis of left femoral vein

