### 5.2.2 Specify inclusion/exclusion criteria for cohort entry and define the index date. Inclusion and exclusion criteria were adapted from the trial as closely as possible. Definitions for all inclusion/exclusion are provided in **Appendix A** and are summarized in the flowcharts below.

#### 5.3 Flowchart of the study cohort assembly

	Optum		Truven		Medicare	
	Less Excluded Patients	Remaining Patients	Less Excluded Patients	Remaining Patients	Less Excluded Patients	Remaining Patients
All patients		77,673,639		200,203,908		6,886,908

Final cohort		11353		17885		49367
Excluded based on Exclusion # 15 - Symptomatic Pulmonary Embolism	-369	11,353	-817	17,885	-1008	49,367
Excluded based on Exclusion # 14 - CYP3A4 Inhibitors	-12	11,722	-28	18,702	-72	50,375
Excluded based on Exclusion # 11 - Malignant Hypertension and based on Exclusion # 12 - Pregnancy	-39	11,734	-116	18,730	-120	50,447
Excluded based on Exclusion # 10 - Active Bleeding/High Risk for Bleeding	-295	11,773	-478	18,846	-1,156	50,567
Excluded based on Exclusion # 9 - CCI	-184	12,068	-155	19,324	-348	51,723
Excluded based on Exclusion # 7 - Liver Disease and based on Exclusion # 8 - Bacterial Endocarditis	-497	12,252	-767	19,479	-1,320	52,071
Excluded based on Exclusion # 6 - CKD stage 4/5/ESRD	-114	12,749	-121	20,246	-496	53,391
Excluded based on Exclusion # 3 - other indications for VKA	-1721	12,863	-2,053	20,367	-9,815	53,887
Excluded based on Exclusion # 2 - Thrombobectomy, Caval Filter	-210	14,584	-335	22,420	-903	63,702
Excluded based on Inclusion # 1 - DVT w/o Symptomatic PE and based on Exclusion # 1 - Age <=18	-117,812	14,794	-168,633	22,755	-499,609	64,605
Excluded based on Use of other NOACs (dabigatran, apixaban, edoxaban)	-5421	132,606	-4267	191,388	-21987	564,214
Excluded based on Gender	0	138,027	0	195,655	0	586,201
Excluded based on Age (missing)	0	138,027	0	195,655	-214	586,201
Excluded based on Age (<65 - Medicare only)	-	-	-	-	-72456	586,415
Excluded due to prior use of exposure and because patient qualified in >1 exposure category	-221,490	138,027	-216,501	195,655	-834,065	658,871
Excluded due to prior use of referent	-516,528	359,517	-684,176	412,156	-3,197,338	1,492,936
Excluded due to insufficient enrollment	-118,721	876,045	-99,207	1,096,332	-232,358	4,690,274
Did not meet cohort entry criteria	-76,678,873	994,766	-199,008,369	1,195,539	-1,964,276	4,922,632

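### Exclusion #14 tests for a claim dated on days -14 to 0, not for supply on hand at initiation, so a current user of an interacting drug who last filled before day -14 stays in the cohort

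*Combined protocol and SAP*

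**What the plan says.** Appendix A, Exclusion #14, gives the trial definition as "Concomitant use of strong CYP3A4 inhibitors (e.g. HIV protease inhibitors, systemic ketoconazole) or strong CYP3A4 inducers rifampin". The claims implementation beside it is a "Prescription claim for following CYP3A inhibitors or strong CYP3A inducers Measured 14 days prior to and also" on the date of initiation. That is 15 calendar days, -14 to 0. The listed inhibitors include "Ketoconazole, itraconazole, voriconazole, telithromycin, clarithromycin, nefazodone, ritonavir, saquinavir" and some further protease inhibitors; the inducers are "Rifampin, rifampicin/rifampin, phenytoin, carbamazepine". Nothing is said about days' supply or about overlap with the index date.

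The flowchart in Section 5.3 labels the step "Excluded based on Exclusion # 14 - CYP3A4 Inhibitors" and shows 12 (Optum), 28 (Truven/MarketScan) and 72 (Medicare) patients removed.

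Section 6.3.2 uses days' supply for one purpose, discontinuation of the index drug: "10 days after the end of the last prescription's days' supply in main analyses". Among the censoring rules, "An added treatment that is not part of the exposure or comparator group does not fulfill this criterion".

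**The concern.** Concomitant use means being on the drug at initiation. A claim dated in a 15-day window is a different test. A patient who filled 30 days of a listed drug on day -20, or 90 days on day -60, has supply on day 0 but no claim in the window, and so enters the cohort.

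No later step corrects this. Table 1 in Appendix B has a row for PGP inhibitors but none for CYP3A4 inhibitors or inducers, so balance between arms on this factor cannot be read from it. Under Section 6.3.2, use of such a drug during follow-up does not censor.

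At stake is fidelity to the trial population. The criterion removes patients whose response to rivaroxaban may be altered by another drug, a factor that could bear on both VTE and bleeding. Section 5.2.2 says the criteria follow the trial as closely as possible, and here a closer version is available from data already held.

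**Working it through.** **Inputs from the documents**
- Window: days -14 to 0, so W = 15 (Appendix A, #14).
- Patients entering the step: 11,734 (Optum), 18,730 (MarketScan), 50,447 (Medicare). Removed: 12, 28, 72 (Section 5.3).
- Final cohort: 11,353 + 17,885 + 49,367 = 78,605 (Section 5.3).
- Matched patients 25,970; pooled risk 18.54 per 1,000; expected events 481.48 (Section 10).

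**Inputs that are assumptions**
- The refill interval S, perfectly regular refilling, and fill dates unrelated to the index date. The documents give none of these, nor do they say which of the 112 were long-term users.

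**1. Reproduce the flowchart step.** 11,734 - 12 = 11,722; 18,730 - 28 = 18,702; 50,447 - 72 = 50,375. All three match the stated figures. In total 12 + 28 + 72 = 112 were removed of 11,734 + 18,730 + 50,447 = 80,911, or 0.14%.

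**2. Share of continuous users missed.** For a patient who refills every S days with the last fill equally likely on any day of the cycle, the chance of no fill in the window is max(0, 1 - W/S). A rule based on supply covering the index date would miss none of these patients under the same assumptions.

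| Refill interval S (days) | Share missed, W = 15 |
|---|---|
| 15 or less | 0% |
| 28 | 1 - 15/28 = 46.4% |
| 30 | 1 - 15/30 = 50.0% |
| 60 | 1 - 15/60 = 75.0% |
| 90 | 1 - 15/90 = 83.3% |

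An even mix of 30- and 90-day fills gives (50.0% + 83.3%)/2 = 66.7%.

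**3. Implied number left in, if all 112 removed were chronic users.** Missed per patient caught = (1 - W/S)/(W/S).
- S = 30: 0.5/0.5 = 1, so 112 × 1 = 112; 112/78,605 = 0.14%.
- S = 90: 0.8333/0.1667 = 5, so 112 × 5 = 560; 560/78,605 = 0.71%.

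If only half of the 112 were chronic users, the range is 56 to 280 (0.07% to 0.36%).

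**4. Weight in the analysis.** Carried proportionally into the matched set, 0.1425% to 0.7124% of 25,970 is about 37 to 185 patients. At 18.54 per 1,000 these contribute about 0.7 to 3.4 of the 481 expected events.

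**5. An illustrative ceiling on the hazard ratio.** Suppose the missed patients are 0.71% of the rivaroxaban arm and their VTE risk is doubled in that arm only. The arm's rate rises by about 0.71%, and a hazard ratio of 0.68 becomes 0.68 × 1.0071 = 0.685.

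**The case against.** The strongest reply is that the miss rate is not a property of the plan. It needs 30- to 90-day fills, perfect refilling and fill dates independent of the index date, and the documents supply none of these. Independence is doubtful: 77.8% of warfarin and 78.3% of rivaroxaban matched patients were hospitalised in the prior 30 days (Appendix B), and the index date is itself a pharmacy fill, so other fills may cluster near it. The list also holds drugs that can be given as short courses, for which the window misses few or none. This stands: 50% to 83% is a conditional range for chronic users only.

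The implementation is also not fully visible. Appendix A refers to an external folder for further detail, and the text does not say whether supply carried into the window counts. A test on the claim date is the plain reading, but it is unconfirmed. That limits certainty; it does not remove the gap in the written rule.

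A reader might go further and infer from the flowchart label, which names inhibitors only, that the inducer list was never applied. The documents do not support that. Appendix A lists the inducers explicitly, and flowchart labels are shortened elsewhere: #9 reads only CCI, and #12 names pregnancy where the rule also covers lactation. The label justifies a separate count and nothing more. If inducers had in fact been left out, the number remaining could exceed 560, but nothing shows this.

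Nor is Section 6.3.2 inconsistent with Exclusion #14. Discontinuation of the index drug is a different task from baseline eligibility. The section shows only that the plan already works with days' supply.

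**Conclusion.** The point holds as a mismatch between criterion and implementation: the trial criterion is use at initiation, and the written rule tests for a claim in days -14 to 0. Its size depends on assumptions. With regular refills every 30 to 90 days, about 50% to 83% of current chronic users of listed drugs would be missed; with fills of 15 days or less, none. If all 112 excluded patients were chronic users, about 112 to 560 more would remain, 0.14% to 0.71% of 78,605, and fewer if many of the 112 were on short courses. It would be too strong to say that the plan is known to retain most chronic users, or that the estimate is biased to any degree that matters: roughly 1 to 3 of 481 expected events are involved. The case for acting is closer emulation at low cost.

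**What to change.** Keep the existing claim window of days -14 to 0. Add a second condition: exclude any patient with a dispensing of a listed inhibitor or inducer in the 180-day baseline whose dispensing date plus days' supply covers the index date. Tying the added condition to the index date keeps it to concomitant use and does not sweep in earlier supply that had already run out.

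Re-run the Exclusion #14 step of the flowchart and report inhibitor and inducer counts separately. If the platform already counts supply carried into the window, say so in Appendix A; the re-run should then change little.

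The cost is one re-coded eligibility step, using dispensing data already held for a baseline period that Section 5.1 already requires, and a refresh of the counts that follow from it. The loss of patients is about 112 to 560 under the assumptions above, and fewer if many of the 112 were short-course users.
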